3.3 Exploratory Endpoints

- 3.3.1 [REDACTED]
[REDACTED]
[REDACTED] [REDACTED] [REDACTED] [REDACTED] [REDACTED] [REDACTED] [REDACTED] [REDACTED]
[REDACTED]
- [REDACTED] [REDACTED]
[REDACTED]
[REDACTED]
[REDACTED]
[REDACTED]
- [REDACTED] [REDACTED]
[REDACTED]
[REDACTED]
- [REDACTED] [REDACTED] [REDACTED] [REDACTED] [REDACTED] [REDACTED] [REDACTED] [REDACTED]
[REDACTED]

4.0 SUBJECT ELIGIBILITY

In order to participate in this study a subject must meet ALL of the eligibility criteria outlined below.

4.1 Inclusion Criteria

- 4.1.1 Written informed consent obtained to participate in the study and Health Insurance Portability and Accountability Act (HIPAA) authorization for release of personal health information (PHI). Consent must be obtained before performance of any study-related procedure not part of normal medical care, with the understanding that consent may be withdrawn by the subject at any time without prejudice to future medical care.
- 4.1.2 Age ≥ 18 years at the time of consent.
- 4.1.3 Documented symptomatic multiple myeloma that has previously responded to therapy (partial response or better) and is relapsed or relapsed and refractory to the last line of therapy. Refractory disease is defined as less than a minimal response or confirmed progressive disease per IMWG criteria within 60 days (measured from the end of the last cycle) after cessation of treatment. Relapsed disease is defined as previously treated disease that progresses and requires initiation of therapy but does not meet criteria for refractory disease.
- 4.1.4 Subjects must have received at least 1 prior line of therapy that includes an IMiD and/or a PI and should have received at least 2 cycles of that regimen.
- 4.1.5 If previously treated with at least 2 consecutive cycles of an anti-CD38 containing regimen, and if refractory to that regimen, the subject must have achieved at least a PR to that line of therapy and must not have received an anti-CD38 mAb for at least 6 months prior to enrollment.
- 4.1.6 Willing and able to adhere to the study visit schedule and other protocol requirements based on the judgement of the investigator.
- 4.1.7 Predicted high risk for severe toxicity from intensive regimens for RRMM, such as standard (full-dose) DPD, DVD, KPD, KRD, Ixa-PD, or Elo-PD as each regimen was published (such regimens often use, for example, twice-weekly bortezomib at 1.3 mg/m^2 , lenalidomide at 25 mg, or pomalidomide 4 mg). High-risk is defined as one of the following:
 - A. Score ≥ 2 (indicating “frail”) on the International Myeloma Working Group instrument (IMWG; Palumbo et al. [Blood 2015]) in Appendix C [17]
 - B. KPS ≤ 70

C. Not meeting criteria A or B above but felt by treating clinician to not be candidate for a standard full-dose regimen on account of one of the following:

- i) History of clinically significant non-hematologic grade ≥ 3 (NCI CTCAE, version 5.0) toxicity attributed to prior anticancer therapy
- ii) History of requiring dose-reduction of at least two separate anticancer drugs during prior therapy for multiple myeloma.

Subjects qualifying for enrollment by criteria (C) should be discussed with study PI before enrollment, to ensure uniform application of this criterion across participating sites.

4.1.8 Measurable disease as defined by one or more of the following:

- A. Monoclonal protein (M-protein) present in serum and/or urine, defined as serum M-protein of ≥ 0.5 g/dL
- B. Urine M-protein of ≥ 200 mg/24 hours
- C. Involved light chain ≥ 10 mg/dL (100 mg/L) AND abnormal serum free light chain ratio.

Subjects without measurable disease (including non-secretory multiple myeloma) will also be eligible to participate if the baseline marrow burden of myeloma is at least 30%.

4.1.9 Subjects who require radiotherapy (which must be localized in its field size) may be enrolled but initiation of study therapy should be deferred until the radiotherapy is completed and 14 days have elapsed since the last date of radiotherapy.

4.1.10 Demonstrate adequate organ function as defined in the table below; all screening labs to be obtained within 72 hours prior to initiating study treatment.

System	Laboratory Value
Hematological*	
Hemoglobin (Hgb)	≥ 8 g/dL Transfusion of packed red blood cells or use of erythropoietin or analogs is permitted, if clinically appropriate, to achieve this threshold.
Absolute Neutrophil Count (ANC)	$\geq 1.0 \times 10^9/L$ Use of growth factors is permitted to fulfill this criterion if neutropenia is felt to be due to MM or due to prior therapy for MM.
Platelets	$\geq 50 \times 10^9/L$ if $< 50\%$ of bone marrow nucleated cells are plasma cells $\geq 30 \times 10^9/L$ if $\geq 50\%$ of BM nucleated cells are plasma cells. Platelet transfusions are permitted to reach entry criteria if thrombocytopenia is felt to be due to MM or due to prior therapy for MM.
Renal*	
Calculated creatinine clearance	Any GFR as long as not currently dialysis-dependent
Hepatic*	
Bilirubin	$\leq 2 \times$ upper limit of normal (ULN). Subjects with Gilbert's syndrome may be enrolled despite a total bilirubin level $> 2 \times$ ULN if their conjugated bilirubin is $< 2 \times$ ULN)
Aspartate aminotransferase (AST)	$\leq 3 \times$ ULN
Alanine aminotransferase (ALT)	$\leq 3 \times$ ULN

*Note: Hematology and other lab parameters that are \geq grade 2 BUT still meet criteria for study entry are allowed. Furthermore, changes in laboratory parameters during the study should not be considered adverse events unless they meet criteria for dose modification(s) of study medication outlined by the protocol and/or worsen from baseline during therapy.

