1.5.2 Clinical Experience

Trial 1 was a phase 2, multicenter, randomized open-label study in patients with relapsed multiple myeloma who were refractory to their last myeloma therapy and had received lenalidomide and bortezomib. Patients were considered relapsed if they had achieved at least stable disease for at least 1 cycle of treatment to at least 1 prior regimen and then developed progressive disease. Patients were considered refractory if they experienced disease progression on or within 60 days of their last therapy. A total of 221 patients were randomized to receive pomalidomide alone or pomalidomide with Low-dose Dex. The results are presented below.

Table 2 Trial 1 Results

	POMALYST^a (n=108)	POMALYST + Low-dose Dex (n=113)
Response		
Overall Response Rate (ORR), ^b n (%)	8 (7.4)	33 (29.2)
95% CI for ORR (%)	(3.3, 14.1)	(21.0, 38.5)
Complete Response (CR), n (%)	0 (0.0)	1 (0.9)
Partial Response (PR), n (%)	8 (7.4)	32 (28.3)
Duration of Response (DOR)		
Median, months	NE	7.4
95% CI for DOR (months)	NE	(5.1, 9.2)

a Results are prior to the addition of dexamethasone.

b ORR = PR + CR per EBMT criteria.

CI, confidence interval; NE, not established (the median has not yet been reached).

Data cutoff: 01 April 2011

Trial 2 was a Phase 3 multi-center, randomized, open-label study, where pomalidomide + Low-dose Dex therapy was compared to High-dose Dex in adult patients with relapsed and refractory multiple myeloma, who had received at least two prior treatment regimens, including lenalidomide and bortezomib, and demonstrated disease progression on or within 60 days of the last therapy. Patients with creatinine clearance ≥ 45 mL/min qualified for the trial. A total of 455 patients were enrolled in the trial: 302 in the pomalidomide + Low-dose Dex arm and 153 in the High-dose Dex arm. Patients in the pomalidomide + Low-dose Dex arm were

administered 4 mg pomalidomide orally on Days 1 to 21 of each 28-day cycle. PFS was significantly longer with pomalidomide + Low-dose Dex than High-dose Dex: HR 0.45 (95% CI: 0.35-0.59 $p < 0.001$). OS was also significantly longer with pomalidomide + Low-dose Dex than High-dose Dex: HR 0.70 (95% CI: 0.54-0.92 $p = 0.009$).

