4.2 Exclusion Criteria

All subjects meeting any of the listed exclusion criteria at baseline will be excluded from study participation.

- 4.2.1 Anti-myeloma treatment within 2 weeks of cycle 1 day 1
- 4.2.2 Subject is refractory to pomalidomide and/or known to be intolerant of pomalidomide at a dose of 3 mg or less.
- 4.2.3 Any monoclonal antibody therapy within the previous 28-days
- 4.2.4 Autologous stem cell transplantation within 12 weeks of day 1 of cycle 1
- 4.2.5 Subjects felt to not be candidates by treating physician for ANY systemic therapy due to excessive comorbidities, frailty, impaired performance status, or other severe limitations. Such limitations can be conceptualized generally as making subjects exceedingly high-risk for ANY systemic treatment. These limitations often stem from medical comorbidities unrelated to MM and they are hence unlikely to improve with MM therapy.
- 4.2.6 Light-chain (AL) amyloidosis. Subjects with secondary amyloidosis due to MM are eligible, providing amyloidosis is not felt to be a clinically significant issue (e.g., amyloid found incidentally on bone marrow core biopsy without evidence of amyloid-mediated organ compromise).
- 4.2.7 Myocardial infarction within 3 months prior to enrollment or has New York Heart Association (NYHA) Class III or IV heart failure (**Appendix N. New York Heart Association Classification of Cardiac Disease**), uncontrolled angina, severe uncontrolled ventricular arrhythmias, or electrocardiographic evidence of acute ischemia or active conduction system abnormalities.
- 4.2.8 Evidence of active bleeding requiring intervention within the last four weeks.
- 4.2.9 Current unstable liver or biliary disease per investigator assessment defined by the presence of ascites, encephalopathy, coagulopathy, hypoalbuminemia, esophageal or gastric varices, persistent jaundice, or cirrhosis. Note: Stable chronic liver disease (including Gilbert's syndrome or asymptomatic gallstones) or hepatobiliary involvement of malignancy is acceptable if patient otherwise meets entry criteria.
- 4.2.10 Any major surgery within the last four weeks

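### The definition of refractory disease in 4.1.3 has no on-treatment limb, so a subject who responded and then had progression confirmed while still on pomalidomide or an anti-CD38 regimen is classed as relapsed

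*Combined protocol and SAP*

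**What the plan says.** Section 4.1.3 of the protocol gives two routes to the refractory class: "Refractory disease is defined as less than a minimal response or confirmed progressive disease per IMWG criteria within 60 days". The second route reads in full: "confirmed progressive disease per IMWG criteria within 60 days (measured from the end of the last cycle) after cessation of treatment". Everything else falls into a residual class: "Relapsed disease is defined as previously treated disease that progresses and requires initiation of therapy but does not meet criteria for refractory disease".

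Two other criteria use the term without defining it or referring back to 4.1.3:

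- 4.2.2 excludes a subject on this ground: "Subject is refractory to pomalidomide and/or known to be intolerant of pomalidomide at a dose of 3 mg or less".
- 4.1.5 sets conditions for a subject treated with at least two consecutive cycles of an anti-CD38 regimen, but only conditionally: "and if refractory to that regimen, the subject must have achieved at least a PR to that line of therapy". It adds a 6-month interval off the antibody.

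Separately, 4.2.3 excludes "Any monoclonal antibody therapy within the previous 28-days", whatever the refractory status.

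The background uses a wider meaning. For the phase 2 pomalidomide trial, section 1.5.2 says: "Patients were considered refractory if they experienced disease progression on or within 60 days of their last therapy". The pomalidomide indication in 1.5.1 is framed in the same way.

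The rationale for Amendment 2, in the Summary of Changes, says that the revised criteria were meant to let in pomalidomide-exposed subjects who are still sensitive to it, and recently anti-CD38-exposed subjects who are still sensitive to that class.

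**The concern.** The 60-day window opens only once treatment has stopped. Progression during treatment, after an initial response, is not mentioned in either limb, and the residual definition then assigns it to the relapsed class. Many myeloma drugs are given until progression, as in this trial (5.8), so progression on drug is an ordinary way for resistance to appear.

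Taken literally, the criteria treat a subject who progresses 30 days after stopping as refractory and one whose progression is confirmed on drug as not refractory. That is the reverse of what a sensitivity requirement should do. Amendment 2 also deleted the blanket 6-month anti-CD38 exclusion and tied the pomalidomide exclusion to the word refractory, so the definition now does the screening.

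At stake are who enters the trial, whether sites apply the criterion alike, and a possible dilution of the overall response rate (ORR), the primary endpoint.

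**Working it through.** **Step 1: apply the definition case by case.** The inputs are 4.1.3, 4.1.5, 4.2.2 and 4.2.3, plus the Appendix O footnote that requires a repeat assessment before a response category, including progressive disease (PD), counts as confirmed. The table assumes that 4.1.3 governs the term throughout. The 4.1.5 column applies to an anti-CD38 regimen given for at least two consecutive cycles.

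| Course on the earlier drug | Less than MR? | Confirmed PD within 60 days after stopping? | Class under 4.1.3 | 4.2.2 (if pomalidomide) | 4.1.5 conditions (if anti-CD38) |
|---|---|---|---|---|---|
| Never reached MR, progressed on drug | Yes | Not needed | Refractory | Excluded | Apply |
| MR or better, PD confirmed 30 days after stopping | No | Yes | Refractory | Excluded | Apply |
| MR or better, PD first seen on drug, confirmed within 60 days after stopping | No | Can be met | Refractory on that reading | Excluded | Apply |
| MR or better, PD confirmed while still on drug | No | No | Relapsed | Not excluded | Do not apply; 28 days under 4.2.3 remains |

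Only the last row falls in the gap.

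**Step 2: compare with the rest of the protocol.** Under the usage in 1.5.2, the last row would be refractory, because that text counts progression on therapy as well as within 60 days of it. Under the Amendment 2 rationale, a subject whose disease progressed on the drug is not one who is still sensitive to it. Both point the opposite way to the literal result.

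**Step 3: reproduce the design.** Inputs from section 10.2: 25 patients in stage 1, stop at 7 or fewer responses; 49 in total, reject at 21 or more; null rate 0.31, alternative 0.48.

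P(reject | p) = Σ over x = 8 to 25 of P[Bin(25, p) = x] × P[Bin(24, p) ≥ 21 − x]

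- p = 0.31: 0.0522, against the stated 0.052.
- p = 0.48: 0.8001, against the stated 0.80.

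The stated operating characteristics are correct. They are conditional on the true response rate, so the wording of 4.1.3 does not alter them.

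**Step 4: illustrate dilution.** The documents give neither the number k of such subjects nor their response rate e. Assume that everyone else responds at the planned 48%, and treat the sample as having the average rate

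p = [0.48 × (49 − k) + e × k] / 49

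For example, k = 5 and e = 0.10 gives (0.48 × 44 + 0.10 × 5) / 49 = 21.62 / 49 = 0.441.

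| k of 49 | e | Overall ORR | Power |
|---|---|---|---|
| 0 | – | 0.480 | 0.80 |
| 5 | 0.10 | 0.441 | 0.62 |
| 5 | 0.20 | 0.451 | 0.67 |
| 5 | 0.30 | 0.462 | 0.72 |
| 8 | 0.10 | 0.418 | 0.49 |
| 8 | 0.20 | 0.434 | 0.58 |
| 8 | 0.30 | 0.451 | 0.67 |

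**The case against.** The strongest reply is that no careful reader would apply 4.1.3 in this way. The parts of that case are:

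- **4.1.5 and 4.2.2 do not cite 4.1.3.** The definition appears where the protocol describes the last line of therapy. If 4.2.2 is read in the sense of 1.5, progression on pomalidomide is excluded. This stands as a limit on the point, which holds only if 4.1.3 governs. But 4.1.3 is the only operative definition in the protocol. If it does not govern, the term is undefined in the two criteria that depend on it, and that needs the same correction.
- **4.1.5 itself contemplates a subject who reached partial response and is refractory to the same regimen.** True, but progression confirmed soon after stopping also fits that description, so it does not supply an on-treatment limb.
- **Eligibility is verified centrally before treatment (11.3).** This weakens any prediction that sites will diverge. It does not cure the wording: the check is against the written criteria, and 11.5.2 bars single-subject eligibility exceptions.
- **Confirmation often comes after the drug is stopped.** This narrows the gap, as the third row of the first table shows. It leaves eligibility depending on when the repeat test was drawn.

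A reader might infer that anyone who progressed while taking pomalidomide or an anti-CD38 antibody gets in. The documents do not support that, because subjects who never reached MR are refractory under the first limb. Nor do they show that the trial will fill with subjects resistant to two of its three drugs. The gap works drug by drug. For anti-CD38 therapy, 4.1.5 is not an outright bar even on a refractory subject: one with a prior partial response and 6 months off the antibody is eligible in any case.

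**Conclusion.** The point holds in a limited form. As written, 4.1.3 classes as relapsed a subject who reached MR or better and had progression confirmed while still on treatment. If 4.1.3 governs, that subject passes 4.2.2 and avoids the conditions of 4.1.5. This is a stated rule that gives a result contrary to the amendment's own aim and to the background usage, so it should be corrected rather than left to interpretation.

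The size is unknown. It would be tempting to say that the trial's power is really 0.5 to 0.7, but the documents do not support that. Those values need 5 or 8 such subjects and response rates of 10–30%, all of which are assumed; with none enrolled, power stays at 0.80. Any dilution lowers the response rate, so the risk is a missed effect and an unintended population, not a false positive.

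**What to change.** Reconcile 4.1.3 with 1.5.1, 1.5.2 and the Amendment 2 rationale. Keep both existing limbs, and in the second insert the words *while on treatment or* directly before "within 60 days (measured from the end of the last cycle) after cessation of treatment". The parenthesis that anchors the 60-day clock must stay; dropping it would be a separate change to eligibility. Then state in 4.1.5 and in 4.2.2 that the 4.1.3 definition applies to the anti-CD38 regimen and to pomalidomide respectively, and carry the wording into the eligibility checklist.

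The cost is a short text change in the next amendment. Some subjects whom a literal reader would have enrolled become ineligible or, for anti-CD38 therapy, must meet the 4.1.5 conditions; their number cannot be estimated from the documents. The sample size and decision rules in 10.2 need no change.

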4.1.11 Male or Female Contraceptive Requirements

a) Male participants

Men must agree to use a latex or synthetic condom during sexual contact with a FCBP even if they have had a vasectomy from the time of signing the informed consent form through 90 days after the last dose of pomalidomide and 5 months after the last dose of isatuximab. These same patients must not donate sperm.

b) Female participants

A female participant is eligible to participate if she is not pregnant, not breastfeeding, and at least one of the following conditions applies:

Not a Female of childbearing potential (FCBP)*,

OR

If an FCBP, participant must have a negative serum or urine pregnancy test with a sensitivity of at least 25 mIU/mL within 10 – 14 days prior to and again within 24 hours of starting pomalidomide and must either commit to continued abstinence from heterosexual intercourse or begin TWO acceptable methods of birth control, one highly effective method and one additional effective method AT THE SAME TIME (Male or Female Contraceptive Requirements), at least 28 days before she starts taking pomalidomide through 90 days after the last dose of pomalidomide and 5 months after the last dose of isatuximab. FCBP must also agree to ongoing pregnancy testing during the entire duration of treatment and monthly for 5 months after the last dose of isatuximab. All patients must be counseled at a minimum of every 28 days about pregnancy precautions and risks of fetal exposure. All patients enrolled into this trial, must be registered in and must comply with all requirements of the POMALYST REMS program.

*A female of childbearing potential (FCBP) is a sexually mature female who: 1) has not undergone a hysterectomy or bilateral oophorectomy; or 2) has not been naturally postmenopausal for at least 24 consecutive months (i.e., has had menses at any time in the preceding 24 consecutive months).

4.1.12 Subject may be HIV+ if the following criterion are met:

1. CD4+ T-cell counts ≥ 350 cells/ μ L
2. No history of AIDS-defining opportunistic infections
3. Subject is on an established antiretroviral therapy (ART) for at least 4 weeks prior to initiation of study treatment.
4. Absence of known, clinically significant drug-drug interactions with isatuximab, pomalidomide, and dexamethasone.

4.1.13 Subjects is willing and able to comply with study procedures based on the judgement of the investigator or protocol designee.

4.2 Exclusion Criteria

All subjects meeting any of the listed exclusion criteria at baseline will be excluded from study participation.

- 4.2.1 Anti-myeloma treatment within 2 weeks of cycle 1 day 1
- 4.2.2 Subject is refractory to pomalidomide and/or known to be intolerant of pomalidomide at a dose of 3 mg or less.
- 4.2.3 Any monoclonal antibody therapy within the previous 28-days
- 4.2.4 Autologous stem cell transplantation within 12 weeks of day 1 of cycle 1
- 4.2.5 Subjects felt to not be candidates by treating physician for ANY systemic therapy due to excessive comorbidities, frailty, impaired performance status, or other severe limitations. Such limitations can be conceptualized generally as making subjects exceedingly high-risk for ANY systemic treatment. These limitations often stem from medical comorbidities unrelated to MM and they are hence unlikely to improve with MM therapy.
- 4.2.6 Light-chain (AL) amyloidosis. Subjects with secondary amyloidosis due to MM are eligible, providing amyloidosis is not felt to be a clinically significant issue (e.g., amyloid found incidentally on bone marrow core biopsy without evidence of amyloid-mediated organ compromise).
- 4.2.7 Myocardial infarction within 3 months prior to enrollment or has New York Heart Association (NYHA) Class III or IV heart failure (**Appendix N. New York Heart Association Classification of Cardiac Disease**), uncontrolled angina, severe uncontrolled ventricular arrhythmias, or electrocardiographic evidence of acute ischemia or active conduction system abnormalities.
- 4.2.8 Evidence of active bleeding requiring intervention within the last four weeks.
- 4.2.9 Current unstable liver or biliary disease per investigator assessment defined by the presence of ascites, encephalopathy, coagulopathy, hypoalbuminemia, esophageal or gastric varices, persistent jaundice, or cirrhosis. Note: Stable chronic liver disease (including Gilbert's syndrome or asymptomatic gallstones) or hepatobiliary involvement of malignancy is acceptable if patient otherwise meets entry criteria.
- 4.2.10 Any major surgery within the last four weeks
- 4.2.11 Diagnosed or treated for another malignancy within 2 years of enrollment, with the exception of complete resection of basal cell carcinoma or squamous cell carcinoma of the skin, an in-situ malignancy, or low-risk prostate cancer after curative therapy. Diagnosis of other prior malignancy within 2 years of enrollment also permissible if no evidence of disease, previously treated with curative intent, and if felt to be unlikely to impact survival during the duration of the study. Other low-risk

malignancies also permissible if natural history or treatment is unlikely to interfere with efficacy or safety endpoints.

4.2.12 Concurrent use of other anti-cancer agents or treatments (with the exception of adjuvant/maintenance hormonal therapy for participants with a history of breast or prostate cancer and other similar agents deemed to have a low likelihood of affecting the outcome of this study (per discretion of treating physician)).

4.2.13 Known to have hepatitis A, B, or C active infection.

Uncontrolled or active HBV infection: Patients with positive HBsAg and/or HBV DNA. Of note:

- Patient can be eligible if anti-HBc IgG positive (with or without positive anti- HBs) but HBsAg and HBV DNA are negative.
 - If anti-HBV therapy in relation with prior infection was started before initiation of IMP, the anti-HBV therapy and monitoring should continue throughout the study treatment period.
- Patients with negative HBsAg and positive HBV DNA observed during screening period will be evaluated by a specialist for start of anti-viral treatment. If HBV DNA becomes negative and all the other study criteria are still met the subject will be eligible.

Active HCV infection: positive HCV RNA and negative anti-HCV. Of note:

- Patients with antiviral therapy for HCV started before initiation of IMP and positive anti-HCV are eligible. The antiviral therapy for HCV should continue throughout the treatment period until seroconversion.
- Patients with positive anti-HCV and undetectable HCV RNA without antiviral therapy for HCV are eligible.

4.2.14 Active systemic infection and severe infections requiring treatment with a parenteral administration of antibiotics.

[figure not shown]
4.2.15 Any clinically significant, uncontrolled medical or psychiatric conditions that, in the Investigator's opinion, would expose the patient to excessive risk or may interfere with compliance or interpretation of the study results.

4.2.16 Known allergy to any of the study medications, their analogues, or excipients in the various formulations of any agent. Hypersensitivity or history of intolerance to steroids, mannitol, pregelatinized starch, sodium stearyl fumarate, histidine (as base and hydrochloride salt), arginine hydrochloride, poloxamer 188, sucrose or any of the other components of study intervention that are not amenable to

- premedication with steroids and H2 blockers or would prohibit further treatment with these agents.
- 4.2.17** Received any investigational drug within 14 days or 5 half-lives of the investigational drug prior to initiation of study intervention, whichever is longer.
- 4.2.18** Subject is receiving prohibited medications or treatments as listed in section 5.7 and **Appendix A. Prohibited Medications or Those to be Used with Caution** of the protocol that cannot be discontinued/replaced by an alternative therapy.
- 4.2.19** Subject does not currently use tobacco products including cigarettes, chew, or smokeless tobacco.

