11.5.2 Single Subject Exceptions

Eligibility single subject exceptions are not permitted for Lineberger Comprehensive Cancer Center Investigator Initiated Trials under any circumstances. Other types of single subject exceptions may be allowed if proper regulatory review has been completed in accordance with Lineberger Comprehensive Cancer Center's Single Subject Exceptions Policy.

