Smoking: In 14 healthy male subjects who smoked 25 cigarettes per day for a total of 10 days, after single oral dose of 4 mg pomalidomide, C_{max} of pomalidomide increased 14% while AUC of pomalidomide decreased 32%, compared to that in 13 healthy male volunteers who were non-smokers.

In Vitro Studies

Pomalidomide does not inhibit or induce CYP450 enzymes or transporters *in vitro*.

Dexamethasone

Below is a partial description of drugs or drug classes that may interact with dexamethasone. Further information can be found at:

<https://medlibrary.org/lib/rx/meds/dexamethasone/page/3/>

Aminoglutethimide

Amphotericin B injection and potassium-depleting agents

Antibiotics

Anticholinesterases

Anticoagulants, Oral

Antidiabetics

Antitubercular Drugs

Cholestyramine

Cyclosporine

Dexamethasone Suppression Test (DST)

Digitalis Glycosides

Ephedrine

Estrogens, including Oral Contraceptives

Hepatic Enzyme Inducers, Inhibitors and Substrates

Ketoconazole

Nonsteroidal Anti-Inflammatory Agents (NSAIDS)

Phenytoin

Thalidomide

Vaccines

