5. In general, how would you rate your satisfaction with your social activities and relationships?					
6. In general, please rate how well you carry out your usual social activities and roles. (This includes activities at home, at work and in your community, and responsibilities as a parent, child, spouse, employee, friend, etc).					

	Never	Rarely	Sometimes	Often	Always
8. How often have you been bothered by emotional problems such as feeling anxious, depressed, or irritable?					

	None	Mild	Moderate	Severe	Very Severe
9. How would you rate your fatigue on average?					

	No Pain 1	2	3	4	5	6	7	8	9	Worst Pain Imaginable 10
10. How would you rate your pain on average?										

IX. Health Behaviors Questionnaire

1. Which of the following describes your smoking habits?

- ☐ I have never smoked (skip to #4)
- ☐ I used to smoke
- ☐ I smoke

2. How many years have you/did you smoke?

years

3. How many packs a day did you/do you smoke?

. packs

4. How often do you do vigorous physical activities for at least 10 minutes that cause heavy sweating or large increases in heart rate or breathing?

- ☐ Never (skip to #6)
- ☐ A few times a month
- ☐ 1-2 times per week
- ☐ 3-4 times per week
- ☐ 5 or more times per week

5. How long do you do these vigorous physical activities each time?

minutes

6. Do you drink alcohol?

- ☐ Yes
- ☐ Almost never
- ☐ No (skip to #9)

7. If you drink alcohol, about how many drinks do you have each week?

drinks

8. What do you drink most often?

- ☐ Beer
- ☐ Red Wine
- ☐ White and red wine
- ☐ Hard liquor (such as bourbon, gin, vodka)
- ☐ All of the above

9. If your parents are still living, how old are they? Or, if either one has passed away, how old was he or she when they died?

Mother

--	--	--

☐ Alive

☐ Deceased

(Current age, or if

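### Exclusion criterion 4.2.19 has the wrong polarity: as written it excludes people who do not use tobacco and leaves only current users eligible.

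*Combined protocol and SAP*

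**What the plan says.** Section 4.2 opens with its operating rule: "All subjects meeting any of the listed exclusion criteria at baseline will be excluded from study participation". The last item in the list, 4.2.19, reads: "Subject does not currently use tobacco products including cigarettes, chew, or smokeless tobacco".

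The item just before it, 4.2.18, shows the form used in the rest of the list. It names the condition that disqualifies: "Subject is receiving prohibited medications or treatments as listed in section 5.7", and continues with a reference to Appendix A.

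Section 11.5.2 closes the route of case-by-case waiver: "Eligibility single subject exceptions are not permitted for Lineberger Comprehensive Cancer Center Investigator Initiated Trials under any circumstances".

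Tobacco appears in only two other places that could bear on the point. Appendix A (section 13.1) summarises label information on smoking and pomalidomide. The global assessment questionnaires (sections 13.10 and 13.11) ask subjects about smoking. Neither section 4.1 nor section 5.7 contains a tobacco criterion.

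**The concern.** An exclusion list works only if each item states what disqualifies. Item 4.2.19 instead states what appears to be a requirement for entry. Under the section 4.2 rule, a subject who satisfies it is removed.

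Three things are at stake.

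- **Who is eligible.** On the literal text, a non-user cannot be enrolled and a current user can.
- **Compliance records.** Section 11.5 requires the study to follow the approved protocol, section 11.3 requires documented confirmation of eligibility, and section 11.4 provides for an audit at least once a year. A checklist that copies 4.2.19 flags every non-user. A checklist that silently reverses it departs from the approved text.
- **The population described in the report.** Unless the direction is settled, a reader cannot tell from the protocol whether current tobacco users were meant to be in or out.

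**Working it through.** No arithmetic applies, so the check is one of logic and cross-reference. The plan gives no figure on this point to reproduce.

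**Step 1: apply the rule.** Section 4.2 excludes a subject if any listed item is true at baseline. Item 4.2.19 is true when the subject is not a current user of tobacco in any form.

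| Tobacco status at baseline | Is 4.2.19 true? | Literal result |
|---|---|---|
| Never used | Yes | Excluded |
| Former user | Yes | Excluded |
| Current user, smoked or smokeless | No | Not excluded by this item |

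Only the third row can pass section 4.2.

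**Step 2: look for text that corrects the result.**

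- Section 4.0 says: "In order to participate in this study a subject must meet ALL of the eligibility criteria outlined below". If this governed the items in 4.2, 4.2.19 would become a requirement to be a non-user. But the same reading would require subjects to satisfy every other item in the list, including recent major surgery and active systemic infection. It cannot be the intended rule for 4.2, and the section's own opening sentence is the specific instruction.
- Sections 4.1 and 5.7 contain no tobacco criterion that would override or explain 4.2.19.
- The summaries for Amendments 1 and 2 do not mention the tobacco item. Amendment 2 revised and renumbered parts of 4.2, and the current text still carries this wording.
- The baseline questionnaire asks "Which of the following describes your smoking habits" and offers never, former and current as answers. It records status and does not decide eligibility.

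Nothing corrects the literal result.

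**Step 3: look for evidence of intent.**

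- *Form.* Of the 19 items in 4.2, the other 18 state a disqualifying condition. Only 4.2.19 is worded as a condition for entry.
- *Content.* Appendix A reports, for smokers after a single dose, "AUC of pomalidomide decreased 32%, compared to that in 13 healthy male volunteers who were non-smokers". The only tobacco-related issue raised anywhere in the protocol therefore concerns users. No reason is given for excluding non-users.

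Both point towards exclusion of current users. Neither states it.

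**Step 4: check what the Appendix A figure can carry.** The comparison is of 14 healthy men who smoked 25 cigarettes a day for 10 days with 13 healthy non-smoking men, after one 4 mg dose. Peak concentration moved the other way, up 14%, and no confidence interval is given for either change. The trial gives repeated doses from a 3 mg start to older or frail patients with myeloma, and 4.2.19 also covers chewing and smokeless tobacco, for which no exposure data are given. The figure helps to show why a tobacco criterion might have been written. It does not give the exposure loss for a smoker in this trial.

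**Step 5: check the design figures.** The two-stage rule, its error rates and the sample size in section 10.2 do not depend on tobacco status and are unaffected.

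**The case against.** The strongest reply is that everyone will know what was meant. The sentence looks like an inclusion statement placed in the wrong list, and no site is likely to recruit tobacco users only. Section 11.3 adds a central safeguard. Sites submit a signed checklist with source documents, and the coordinating centre verifies final eligibility for every subject before treatment. The checklist is not among the documents and may already state the intended direction.

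Much of this stands. The literal reading would probably not be followed, and central verification makes divergent practice between sites less likely. It does not remove the defect. The person verifying eligibility must still apply a sentence that says the reverse of what was probably intended, and section 11.5.2 leaves no discretion to set it aside.

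A reader might also infer three stronger things that the documents do not support.

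- *That each smoker enrolled would have about one third less pomalidomide exposure.* The 32% comes from the small, single-dose, healthy-volunteer comparison described above. It cannot be assigned to individual patients or to users of smokeless tobacco.
- *That the primary response rate would be biased by some amount.* The protocol gives no relation between exposure and response and no expected share of tobacco users. Section 10.2 allows for a somewhat lower response rate because of the 3 mg start but says nothing about smoking. No effect on response rate can be derived.
- *That subjects already enrolled are in violation.* Enrolment to date and the checklist wording are not visible, so any actual violation is conditional on both.

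**Conclusion.** The criterion is wrong as written. Section 4.2 and item 4.2.19, read together, exclude non-users of tobacco and leave only current users eligible, and no other text in force corrects this. It is an internal contradiction in eligibility, not a methodological choice that could be defended.

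The size is categorical. On the literal text, the item decides eligibility for all 49 planned subjects. That is an upper bound, because the number affected in practice depends on how the checklist is worded and applied.

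The conclusion that the polarity is wrong rests on the text alone. The further conclusion that exclusion of current users was meant is an inference from the form of the sentence and the content of Appendix A, and only the sponsor can confirm it. The case for correction rests on the contradiction and the bar on exceptions. It does not rest on any claim about drug exposure or response rate.

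**What to change.** 1. The sponsor confirms in writing which group 4.2.19 is meant to exclude.
2. The item is then reconciled with the section 4.2 rule. If current users are to be excluded, either reword it so that it names current tobacco use as the disqualifying condition, or move the present sentence unchanged to section 4.1 as an inclusion criterion. One of these is enough.
3. The eligibility checklist used for verification under section 11.3 is brought into line with the amended text.
4. Subjects already enrolled are checked against the corrected criterion, and any departures are recorded under section 11.5.3.

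The cost is a one-line amendment, a checklist update and a review of tobacco status for subjects already enrolled. Sample size, stopping rules and analyses do not change.
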